ANNEX 3. ADDITIONAL INFORMATION

[figure not shown]
Clinical Frailty Scale- Spanish Translation (19)

1. **En muy buena forma.** Personas que están fuertes, activas, vigorosas y motivadas. Son personas que suelen practicar ejercicio con regularidad. Son de los que están en mejor forma para su edad.
2. **En forma.** Personas **sin síntomas de enfermedad activa**, pero que están menos en forma que las de la categoría 1. Suele ocurrir que se ejercitan o están **muy activas por temporadas**, por ejemplo, según la estación.
3. **En buen estado.** Personas que tienen **bien controlados sus problemas médicos**, pero que **no llevan actividad física regular** más allá de los paseos habituales.
4. **Vulnerables.** Aunque **no dependen de otros** que les ayuden en la vida diaria, a menudo **los síntomas limitan sus actividades**. Suelen quejarse de estar «lentos» o cansados durante el día.
5. **Levemente frágiles.** Estas personas a menudo tienen un **enlentecimiento más evidente** y necesitan ayuda para las **actividades de la vida diaria importantes** (economía, transporte, labores domésticas, medicación). Es típico que la fragilidad leve vaya dificultando salir solos de compras o a pasear y hacer la comida o las tareas del hogar.
6. **Moderadamente frágiles.** Personas que necesitan ayuda para **todas las actividades en el exterior** y para realizar las **tareas domésticas**. En casa, suelen tener problemas con las escaleras y necesitan **ayuda con el baño**, y pueden requerir alguna asistencia para vestirse (guía y acompañamiento).
7. **Con fragilidad grave.** **Dependen totalmente para el cuidado personal**, sea cual fuere la causa (física o cognitiva). Aun así, parecen estables y sin riesgo de muerte (en los siguientes ~6 meses).
8. **Con fragilidad muy grave.** Totalmente dependientes, se acercan al final de la vida. Es típico que ni siquiera se recuperen de afecciones menores.
9. **Enfermo terminal.** Se aproximan al final de la vida. Esta categoría se aplica a personas con **esperanza de vida < 6 meses y sin otros signos de fragilidad**.

En personas con demencia, el grado de fragilidad se corresponde con el grado de demencia. **Son síntomas comunes de demencia leve** olvidar los detalles de un acontecimiento reciente aun recordando el evento en sí, la repetición de una misma pregunta o relato y el aislamiento social. En la **demencia moderada**, la memoria reciente está muy afectada, aunque parezca que recuerdan bien los acontecimientos de su pasado. Con pautas, pueden cuidarse solos. En la **demencia grave**, no son posibles los cuidados personales sin ayuda.

[figure not shown]
P. Díez-Villanueva et al/Rev Esp Cardiol. 2019;72(1):63-71(Clinical Frailty Scale. Reproduced with permission of Rockwood et al (21)

EHRA scoring related-symptoms (23)

[figure not shown]

NYHA classification of heart failure (24)

Comorbidities Charlson Index (25)

1. ABBREVIATIONS

ACE	Angiotensin Converting Enzyme inhibitors
ADR	Adverse Drug Reaction
AF	Atrial Fibrillation
AIDs	Acquired immune deficiency syndrome
ALT	Alanine Aminotransferase
ARB	Angiotensin-Receptor Blockers
AST	Aspartate Aminotransferase
BI	Boehringer Ingelheim
BID	Twice a day
BMI	Body Mass Index
CABG	Coronary Artery Bypass Grafting
CCI	Charlson Comorbidity Index
CFS	Clinical Frailty Scale
CHA2DS2-VASc	Congestive heart failure, Hypertension, Age (> 75), Diabetes mellitus, Stroke/TIA, Vascular disease, Age 65-74, Sex Category
CI	Confidence Interval
CKD	Chronic Kidney Disease
CRF	Case Report Form
eCRF	Electronic Case Report Form
EHRA	European Heart Rhythm Association
GFR	Glomerular Filtration Rate
HAS-BLED	Hypertension, Abnormal renal and liver function, Stroke (1 point), Bleeding history or predisposition, Labile INR, Elderly (>65 years), Drugs and Alcohol.
ICH	Intracranial haemorrhage
ICH-GCP	Harmonized Tripartite Guideline for Good Clinical Practice
INR	International Normalized Ratio
LVEF	Left ventricular ejection fraction
NSAIDs	Nonsteroidal Anti-Inflammatory Drugs
NYHA	New York Heart Association
NOAC	Non-vitamin K antagonist oral anticoagulant
NVAF	Non-valvular atrial fibrillation
OAC	Oral anticoagulant
PCI	Percutaneous coronary intervention

Document: H:\HOR-Europe\2019\2512352 - Study on anticoagulation management - BI\Proyecto\Estadistica\SAP\S AP_REBELD_version1.0_08072020.docx

Author: [REDACTED] Version Number: Version 1.0
Version Date: [08072020]

Template No.: RWI_TP_BIOS0013 Revision 1

Reference: RWI_WI_BIOS0015

Effective Date: 15Jun2018

PT	Preferred Terms
QD	Once a day
SADR	Serious Adverse Drug Reaction
SAHS	Sleep apnoea-hypopnoea syndrome
SAP	Statistical Analysis Plan
SmPC	Summary of Product Characteristics
SOC	System Organ Classes
SOPs	Standard Operating Procedures
TIA	Transitory ischemic attack
TLF	Tables/Listings/Figures
VKA	Vitamin K Antagonist

Document: H:\HOR-Europe\2019\2512352 - Study on anticoagulation management - BI\Proyecto\Estadistica\SAP\SAP_REBELD_version1.0_08072020.docx

Author: [Redacted]

Version Number: Version 1.0

Version Date: [08072020]

Template No.: RWI_TP_BIOS0013 Revision 1

Reference: RWI_WI_BIOS0015

Effective Date: 15Jun2018

2. INTRODUCTION

This statistical analysis plan (SAP) describes the rules and conventions to be used in the presentation and analysis of treatment patterns and patient profile. It describes the data to be summarized and analyzed, including specifics of the statistical analyses to be performed.

This statistical analysis plan (SAP) is based on protocol version 1.0, dated 24 May 2019 and case report forms (CRFs) version 2, dated 10 March 2020.

3. STUDY OBJECTIVES

This study has been designed in order to describe the current non-vitamin K antagonist oral anticoagulants (NOACs) management in elderly patients in Spain.

3.1 Primary Objectives

The primary objective is to describe the pattern of usage of NOACs prescribed according to their Summary of Product Characteristics (SmPC), by current NOAC type and dose, in elderly patients (≥ 75 years-old) with non-valvular atrial fibrillation (NVAf) at the time of the study visit.

3.2 Secondary Objectives

The secondary objectives are:

1. To describe patients' characteristics at the time of the study visit by current NOAC type stratified by duration since first NOAC initiation.
2. To describe OAC treatment management since first NOAC initiation until the study visit by duration since first NOAC initiation: previous vitamin K antagonists (VKA) treatment, first NOAC treatment duration, dose changes, switch between NOACs and

Document:	H:\HOR-Europe\2019\2512352 - Study on anticoagulation management - BI\Proyecto\Estadistica\SAP\SAP_REBELD_version1.0_08072020.docx		
Author:	██████████	Version Number:	Version 1.0
		Version Date:	[08072020]

Template No.: RWI_TP_BIOS0013 Revision 1

Reference: RWI_WI_BIOS0015

Effective Date: 15Jun2018

reasons for switch, total NOAC treatment duration and additional antiplatelet treatment.

3. To describe the Clinical Frailty Scale grading, CFS (1), at the time of the study visit, by current NOAC type.
4. To describe first NOAC usage by NOAC type, for primary prevention or secondary prevention, at the time of first NOAC initiation.

Further objective: To evaluate the appropriateness of prescribed therapy based on Spanish health authorities' recommendations (2) (therapeutic positioning report) and other regional guidelines by NOAC type (if there are enough patients for a NOAC type), at the time of first NOAC initiation.

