8. RESEARCH QUESTION AND OBJECTIVES

This study has been designed in order to describe the current non-vitamin K antagonist oral anticoagulants (NOACs) management in elderly patients in Spain.

Primary objective: To describe the pattern of usage of NOACs prescribed according to their Summary of Product Characteristics (SmPC), by current NOAC type and dose, in elderly patients (≥ 75 years-old) with non-valvular atrial fibrillation (NVAF) at the time of the study visit.

Secondary objectives:

1. To describe patients characteristics at the time of the study visit by current NOAC type stratified by duration since first NOAC initiation.
2. To describe OAC treatment management since first NOAC initiation until the study visit by duration since first NOAC initiation: previous vitamin K antagonists (VKA) treatment, first NOAC treatment duration, dose changes, switch between NOACs and reasons for switch, total NOAC treatment duration and additional antiplatelet treatment.
3. To describe the Clinical Frailty Scale grading, CFS ([19](#)), at the time of the study visit, by current NOAC type.
4. To describe first NOAC usage by NOAC type, for primary prevention or secondary prevention, at the time of first NOAC initiation.

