9. OUTPUT PRESENTATIONS

Tables and Figures on page 42 describe the presentations for this study and therefore the format and content of the summary TLFs to be provided by [REDACTED]

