14.3.1 Patient's characteristics

Patient's characteristics at the time of the study visit will be summarized descriptively by current NOAC type. Patients will be also stratified by duration since the first NOAC initiation until the study visit date (>4 months / ≤ 4 months). All covariates related to patient's characteristics (refer to Section 11 , Table 3.) will be analyzed descriptively by NOAC type and by the duration since the first NOAC initiation. Standardized differences between Pradaxa® and other NOACs will be estimated for these covariates. For this, a minimum of 50 patients is required for each group.

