17.2.1 Patient's characteristics according to current NOAC type

Table 7. Socio-demographic variables and habits according to current NOAC type

		Dabigatran	Rivaroxaban	Apixaban	Edoxaban	Total	Standardized differences (Pradaxa® vs others)
Age	Valid N Mean (SD) Median (Q1-Q3) Min-Max N missing						
Age group	Valid N 75-79 years 80-84 years ≥85 years N missing						
Sex	Valid N Male, n (%) Female, n (%) N missing						
Weight (Kg)	Valid N Mean (SD) Median (Q1-Q3) Min-Max N missing						
Weight (Kg) cat	Valid N ≤60 kg, n (%) >60 kg, n (%) N missing						
Height (cm)	Valid N Mean (SD)						

Document: H:\HOR-Europe\2019\2512352 - Study on anticoagulation management - BI\Proyecto\Estadistica\SAP\S AP_REBELD_version1.0_08072020.docx

Author: [REDACTED] Version Number: Version 1.0
Version Date: [08072020]

Template No.: RWI_TP_BIOS0013 Revision 1

Reference: RWI_WI_BIOS0015

Effective Date: 15Jun2018

		Dabigatran	Rivaroxaban	Apixaban	Edoxaban	Total	Standardized differences (Pradaxa® vs others)
	Median (Q1-Q3) Min-Max N missing						
BMI (Kg/m2)	Valid N Mean (SD) Median (Q1-Q3) Min-Max N missing						
BMI cat	Valid N Underweight: BMI < 18.5 kg/m2 Normal weight: 18.5 kg/m2 <= BMI <= 25 kg/m2 Overweight: 25 kg/m2 < BMI <= 30 kg/m2 Obese: 30 kg/m2 < BMI <= 35 kg/m2 Severely Obese: BMI > 35 kg/m2 N missing						
Caregiver	Valid N No Yes N missing						
Place where patients is living	Valid N Home alone At home with partner/other family member/a friend Other's home (e.g. family member's) Nursing home N missing						
Smoking habit	Valid N Ex-smoker						

Document: H:\HOR-Europe\2019\2512352 - Study on anticoagulation management - BI\Proyecto\Estadistica\SAP\S AP_REBELD_version1.0_08072020.docx

Author: [REDACTED]

Version Number:

Version 1.0

Version Date:

[08072020]

Template No.: RWI_TP_BIOS0013 Revision 1

Reference: RWI_WI_BIOS0015

Effective Date: 15Jun2018

		Dabigatran	Rivaroxaban	Apixaban	Edoxaban	Total	Standardized differences (Pradaxa® vs others)
	Smoker Non-smoker N missing						
Alcohol consumption	Valid N Casual Habitual Abuse Dependence N missing						

Table 8. Analytical laboratory results from the last available blood sample analysis according to current NOAC type

		Dabigatran	Rivaroxaban	Apixaban	Edoxaban	Total	Standardized differences (Pradaxa® vs others)
Serum creatinine (mg/dl)	Valid N Mean (SD) Median (Q1-Q3) Min-Max N missing						

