17.2.2 Patient's characteristics according to duration since the first NOAC initiation

Table 17. Socio-demographic variables and habits according to duration since the first NOAC initiation

		≤4 months	>4 months	Total
Age	Valid N Mean (SD) Median (Q1-Q3) Min-Max N missing			
Age group	Valid N 75-79 years 80-84 years ≥85 years N missing			
Sex	Valid N Male, n (%) Female, n (%) N missing			
Weight (Kg)	Valid N Mean (SD) Median (Q1-Q3) Min-Max N missing			
Weight (Kg) cat	Valid N ≤60 kg, n (%) >60 kg, n (%) N missing			
Height (cm)	Valid N Mean (SD) Median (Q1-Q3) Min-Max N missing			
BMI (Kg/m2)	Valid N Mean (SD) Median (Q1-Q3) Min-Max N missing			

Document: H:\HOR-Europe\2019\2512352 - Study on anticoagulation management - BI\Proyecto\Estadística\SAP\S
AP_REBELD_version1.0_08072020.docx

Author: [REDACTED] Version Number: Version 1.0
Version Date: [08072020]

Template No.: RWI_TP_BIOS0013 Revision 1

Reference: RWI_WI_BIOS0015

Effective Date: 15Jun2018

		≤4 months	>4 months	Total
BMI cat	Valid N Underweight: BMI< 18.5 kg/m ² Normal weight: 18.5 kg/m ² ≤ BMI≤ 25 kg/m ² Overweight: 25 kg/m ² < BMI≤ 30 kg/m ² Obese: 30 kg/m ² <BMI≤ 35 kg/m ² Severely Obese: BMI> 35 kg/m ² N missing			
Caregiver	Valid N No Yes N missing			
Place where patient is living	Valid N Home alone At home with partner/other family member/a friend Other's home (e.g. family member's) Nursing home N missing			
Smoking habit	Valid N Ex-smoker Smoker Non-smoker N missing			
Alcohol consumption	Valid N Casual Habitual Abuse Dependence N missing			

Document: H:\HOR-Europe\2019\2512352 - Study on anticoagulation management - BI\Proyecto\Estadística\SAP\S
AP_REBELD_version1.0_08072020.docx

Author: Version Number: Version 1.0
Version Date: [08072020]

Template No.: RWI_TP_BIOS0013 Revision 1

Reference: RWI_WI_BIOS0015

Effective Date: 15Jun2018

Table 18. Analytical laboratory results from the last available blood sample analysis according to duration since the first NOAC initiation

		≤4 months	>4 months	Total
Serum creatinine (mg/dl)	Valid N Mean (SD) Median (Q1-Q3) Min-Max N missing			
Serum creatinine Normal levels: 0.6-1.2 mg/dl in males 0.5-1.1 mg/dl in females	Valid N Normal levels High/low level N missing			
Creatinine clearance (ml/min)	Valid N Mean (SD) Median (Q1-Q3) Min-Max N missing			
Creatinine clearance (ml/min): Cockcroft and Gault formula	Valid N Mean (SD) Median (Q1-Q3) Min-Max N missing			

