*Only patients who stopped second NOAC treatment

Table 39. will be repeated for each treatment switch during follow-up.

Document: H:\HOR-Europe\2019\2512352 - Study on anticoagulation management - BI\Proyecto\Estadística\SAP\S
AP_REBELD_version1.0_08072020.docx

Author: [REDACTED]

Version Number:

Version 1.0

Version Date:

[08072020]

Template No.: RWI_TP_BIOS0013 Revision 1

Reference: RWI_WI_BIOS0015

Effective Date: 15Jun2018

Table 40. Total time (in years) in NOAC treatment

		≤4 months	>4 months	Total
Total time in NOAC treatment (in years)	Valid N Mean (SD) Median (Q1-Q3) Min-Max N missing			
Total time in NOAC treatment (cat)	Valid N <1 year 1-2 years 2-3 years >3 years N missing			

Table 41. History and current antiplatelet treatment according to duration since the first NOAC initiation

		≤4 months	>4 months	Total
Antiplatelet treatments received (all)	Valid N Aspirin Clopidogrel Prasugrel Ticlopidine Ticagrelor Cilostazol Triflusal Dipyridamole Others N missing			
Time in treatment with antiplatelet agents (in years)	Valid N Mean (SD) Median (Q1-Q3) Min-Max N missing			
Current antiplatelet treatment (at study visit)	Valid N None			

Document: H:\HOR-Europe\2019\2512352 - Study on anticoagulation management - BI\Proyecto\Estadistica\SAP\S AP_REBELD_version1.0_08072020.docx

Author: [REDACTED] Version Number: Version 1.0
Version Date: [08072020]

Template No.: RWI_TP_BIOS0013 Revision 1

Reference: RWI_WI_BIOS0015

Effective Date: 15Jun2018

		≤4 months	>4 months	Total
	Aspirin			
	Clopidogrel			
	Prasugrel			
	Ticlopidine			
	Ticagrelor			
	Cilostazol			
	Triflusal			
	Dipyridamole			
	Others			
	N missing			

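### Secondary objective 1 asks for patient characteristics by NOAC type within duration strata, but the table shells give type and duration only separately, and the 4-month cut is too narrow to carry the crossing

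*SAP*

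**What the plan says.** Protocol section 8 states the first secondary objective as "To describe patients characteristics at the time of the study visit by current NOAC type stratified by duration since first NOAC initiation". SAP 3.2 repeats it, again asking for characteristics "by current NOAC type stratified by duration since first NOAC initiation". On its face this is a crossed description: NOAC type within strata of duration.

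The analysis text in SAP 14.3.1 is looser. It summarises characteristics by current NOAC type and adds "Patients will be also stratified by duration since the first NOAC initiation until the study visit date", cut at 4 months. It then says the covariates "will be analyzed descriptively by NOAC type and by the duration since the first NOAC initiation". SAP 8.5 lists the same two duration groups as a subgroup analysis for this objective and requires at least 50 patients per subgroup.

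SAP section 9 says the tables and figures "describe the presentations for this study and therefore the format and content of the summary TLFs to be provided by" the analysis provider, so the shells are the specification. Section 17.2.1 opens with "Table 7. Socio-demographic variables and habits according to current NOAC type" and runs to Table 16, with four NOAC columns, a total and a standardized difference. Section 17.2.2 presents "characteristics according to duration since the first NOAC initiation" in Tables 17-26, with columns for ≤4 months, >4 months and total.

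**The concern.** A programmer who follows the SAP will produce every table in section 17.2 and still not have the description named in the objective. SAP 4.6, which lists departures from the protocol, does not mention it.

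The standardized differences between Pradaxa and the other NOACs, which protocol 9.9 names as the tool for assessing channeling, appear only in Tables 7-16, pooled over all durations. If the NOACs differ in time since initiation, which is plausible but not documented, those pooled differences also carry differences in time on treatment. No visible shell reports time since first NOAC by current NOAC, so a reader could not tell whether this happens.

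The cut-point adds a second difficulty. With entry restricted to patients who started at least 3 months earlier, one of the two planned strata can hold only patients between 3 and 4 months after initiation.

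**Working it through.** **Objective against shells.** The plan states no figure on this point, so the first check sets the documents side by side.

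| Output | Split by NOAC type | Split by duration |
|---|---|---|
| Table 6 (counts) | yes, own rows | yes, own rows, not crossed |
| Tables 7-16 (10 tables) | yes | no |
| Tables 17-26 (10 tables) | no | yes |
| Crossed characteristics tables | none | none |

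Numbering from 7 to 26 is unbroken, so redaction does not hide a characteristics table. The one number missing among the visible tables, 44, comes after the prevention-strategy table and outside section 17.2.

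**Width of the ≤4-month stratum.** SAP 7.2.7 converts days to months by dividing by 30.5. Four months is 4 × 30.5 = 122 days. The 3-month entry criterion is about 3 × 30.5 = 91.5 days. The window is 122 − 91.5 = 30.5 days.

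**What a crossing at 4 months would need.** Inputs: about 500 patients (SAP 4.2), four NOACs, two strata and a minimum of 50 (SAP 8.5). Applying the minimum to each crossed cell is my reading; the SAP does not discuss crossed cells. Eight cells × 50 = 400 patients, of whom 4 × 50 = 200 must be in the ≤4-month stratum: 200/500 = 40%.

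**What the window might hold.** The documents give no distribution of time since first NOAC, so these are assumptions.

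Uniform from 3 months to an upper limit, share = 30.5 / (years × 365.25 − 91.5):
- 1 year: 30.5/273.75 = 11.1%, about 56 of 500
- 2 years: 30.5/639 = 4.8%, about 24
- 3 years: 30.5/1004.25 = 3.0%, about 15
- 5 years: 30.5/1734.75 = 1.8%, about 9

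Exponential beyond 3 months, share = 1 − exp(−1/(mean − 3)):
- overall mean 24 months: 1 − exp(−1/21) = 4.7%, about 23 of 500
- overall mean 36 months: 1 − exp(−1/33) = 3.0%, about 15

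With equal NOAC shares, the most favourable case gives 56/4 = 14 per NOAC. In every other case the whole ≤4-month stratum is below 50.

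**Two broader bands, <24 and ≥24 months.** Same exponential assumption and equal NOAC shares, so 500/4 = 125 per NOAC. Share below 24 months = 1 − exp(−21/(mean − 3)):
- mean 24: 1 − exp(−21/21) = 63.2%, giving 79 and 46 per NOAC
- mean 36: 1 − exp(−21/33) = 47.1%, giving 59 and 66 per NOAC

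Cells run from about 46 to 79. The lowest is just under 50, so a fallback rule is needed even here.

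**The case against.** The strongest reply is that the objective is shorthand and the analysis text governs. SAP 14.3.1 adds duration with an also and joins the two factors with an and. Two separate breakdowns is a natural reading, and the shells deliver exactly that. This stands as far as it goes: 14.3.1 is ambiguous, and a reader who infers that the SAP text rules out the crossed analysis goes too far. It does not reconcile the shells with an objective that both documents state in crossed form, and 4.6 is silent.

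A second reply is that crossing at 4 months would add almost nothing. This also stands. If 3-5% of patients are in the short stratum, tables within the >4-month stratum would nearly reproduce Tables 7-16. It argues against the cut, not against answering the objective.

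A third is that re-banding departs from a split set in the protocol's own outcome definition (9.3.2.2), in a SAP dated 8 July 2020, after the planned end of data collection on 27 April 2020. That is a real cost, and it is why the change must be declared and fixed before results by NOAC are seen.

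It is tempting to borrow the four year bands of Table 40. That does not work. Four bands × four NOACs × 50 = 800 patients, more than the study has. Table 40 also bands total treatment time, which under SAP 7.2.11 leaves out interruptions, whereas the objective concerns time since first initiation.

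**Conclusion.** The point holds as a mismatch between a stated secondary objective and its specified outputs. As planned, characteristics by NOAC type within duration strata are not tabulated, and the change is not declared.

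The ≤4-month stratum would probably miss the 50-patient minimum as a whole: about 9 to 56 of 500 under the assumptions above. All four NOACs could reach 50 there only if at least 40% of patients fell in a one-month window. These counts rest on assumed duration distributions, and the per-NOAC figures also on equal NOAC shares.

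A reader might infer that the objective exists to separate the effect of the drug from time on the drug, or that the planned NOAC comparisons are confounded by duration. The documents support neither. They give no such purpose, the study is descriptive, and nothing in them shows that NOAC type and duration are related. The consequence is limited to one descriptive secondary objective left unanswered as worded.

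**What to change.** 1. Keep the protocol's 4-month split as a count, shown by NOAC type in Table 6.
2. Add shells that repeat Tables 7-16 within two broader bands of time since first NOAC initiation, using the SAP 7.2.7 variable, for example <24 and ≥24 months.
3. Fix the bands before any results by NOAC are seen.
4. Apply the 50-patient minimum to each NOAC-by-band cell. Where a cell is too small, show Pradaxa versus other NOACs within the band, with the standardized difference.
5. Declare the bands, the minimum and the fallback in SAP 4.6.

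If the sponsor does not want crossed tables, 4.6 should instead restate the objective as two separate breakdowns.

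The cost of the first route is up to 10 tables × 2 bands = 20 extra table panels and a declared cut chosen after the protocol. The first NOAC start date and the study visit date are already collected, so no new data are needed. The second route costs one entry in 4.6, but gives up the stratified description.
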